### **Laboratory Measurements (in alphabetical order)**

Blood chemistry, Complete Blood Count (CBC), and Urinalysis are obtained to assess for adverse events. Enzyme levels will be obtained once at baseline and end of the study.

Pregnancy Testing. Urine pregnancy tests will be obtained from all women at baseline, week 5, week 9, and end of study.

Urine Drug Screen and Urine Buprenorphine and Norbuprenorphine Screen. Quantitative urine buprenorphine and norbuprenorphine levels (using gas chromatography) with urine creatinine used as a control for urinary concentration will be assessed twice weekly throughout the trial. Urinary buprenorphine levels have been used extensively to establish buprenorphine adherence (Fox, Tetlow, and Allen 2006; Vincent et al. 1999). Quantitative levels of methadone have been used successfully to establish methadone compliance in a methadone maintenance program (Preston et al. 2003). Our toxicology consultant will assist us in interpreting urine creatinine controlled quantitative buprenorphine levels to establish medication adherence. Data from this trial will be used in optimizing the use of quantitative urine buprenorphine and norbuprenorphine levels in the subsequent efficacy trial. Qualitative (emit) urine toxicology for other drugs (benzodiazepines, barbiturates, opiates, marijuana, methadone, and amphetamine) is done at baseline and weekly throughout the trial.

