## **3.4 Study Endpoints**

### **3.4.1 Primary Study Endpoint**

For the ROD group, we will calculate the within-patient proportion of study days on which video captured adherence, as per protocol.

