### **Secondary Study Endpoints**

We will use a combination of self-report and (nor)buprenorphine levels to classify patients in the AC group as adherent or non-adherent for each study day to compare their rates of adherence to the (video-verified) rates in the ROD group. These comparisons will give a direct estimate of the improvement in adherence likely to be observed between the proposed method and standard methods.

Rates of illicit opiate use will be compared between the groups using combinations of urine drug screens (UDS) and TLFB self-reports obtained at each visit.

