### **5.2.3 Visits 5-28**

Patients will be seen twice weekly. For each in-office visit, patients will provide a urine sample that will be tested for drugs of abuse and for quantitative buprenorphine and norbuprenorphine levels. At each office visit, patients will also complete questionnaires about craving and depression. They will be asked about other medications they are using, about their drug and alcohol use since their last visit, and about any side effects they may be experiencing. Dosage adjustments will be made as needed at the discretion of their clinician. Subjects will also participate in weekly, manualized Medication Management. After induction, all patients will receive open-label Suboxone® for 12 weeks. Patients in both groups will receive a weeks' worth of Suboxone® at each medication management visit. After the 12 weeks of Suboxone®, subjects will be referred to on-going treatment options in the community.

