## **6.2 Statistical Methods**

For the ROD group, we will calculate the within-patient proportion of study days on which video captured adherence, as per protocol. We will use these data to compare observed adherence rates in this group to rates reported in prior studies. The primary comparison between the groups will use the creatinine normalized weekly quantitative urine levels for buprenorphine and norbuprenorphine. Exploratory analyses include the following: We will use a combination of self-report and (nor)buprenorphine levels to classify patients in the AC group as adherent or non-adherent for each study day, and use mixed effects logistic regression models to compare their rates of adherence to the (video-verified) rates in the ROD group. Rates of illicit opiate use will be compared between the groups using combinations of urine drug screens(UDS) and TLFB self-reports obtained at each visit. The ASI, CGI, and HAM-D scales are obtained monthly. To assess usability and acceptability of the ROD protocol and text messaging application, [name] will conduct semi-structured interviews and analyze data from the Systems Usability Scale (SUS) at the final office visit.

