### **6.3.2 Analysis of Primary Outcome of Interest**

The primary comparison between the groups will use the creatinine normalized weekly quantitative urine levels for buprenorphine and norbuprenorphine. For each response, we anticipate that a response transformation, such as the log transform, will yield responses appropriate for group comparisons based on linear mixed effects models, but we will consider generalized linear mixed effects models if necessary. Comparisons of BIC statistics across different covariance structures will be used to select the best model for within subject correlations – typically a model with random intercept and ar(1) residual correlations provides a good fit. The main explanatory variable will be a binary indicator for group (ROD vs AC). Time will be regarded as a continuous scale, and linear, quadratic or spline trends will be used as necessary, with group by time interactions examined for significance. Our primary analyses will examine the two sets of responses (buprenorphine and norbuprenorphine) separately, but we will also consider bivariate mixed effects models with cross-correlation structure to assess strength of dependence and concordance between the two sets of measures. These analyses will be performed using PROC GENMOD in SAS.

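### The ROD-versus-AC adherence contrast rests on control-only adherence calls, with no stated urine cut-off and no described masking

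*Combined protocol and SAP*

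**What the plan says.** - **Urine interpretation (3.3, Laboratory Measurements).** Buprenorphine and norbuprenorphine are measured twice weekly in all patients. On turning levels into adherence: "Our toxicology consultant will assist us in interpreting urine creatinine controlled quantitative buprenorphine levels to establish medication adherence". The section adds: "Data from this trial will be used in optimizing the use of quantitative urine buprenorphine and norbuprenorphine levels in the subsequent efficacy trial". No concentration, ratio or creatinine-adjusted cut-off is stated there or elsewhere.
- **Who is classified (3.4, repeated in 5.6).** Self-report and levels will be combined to "classify patients in the AC group as adherent or non-adherent for each study day". For the other arm, 3.4.1 says: "For the ROD group, we will calculate the within-patient proportion of study days on which video captured adherence, as per protocol".
- **Analysis (6.2).** The plan is to "use mixed effects logistic regression models to compare their rates of adherence to the (video-verified) rates in the ROD group". This follows the words "Exploratory analyses include the following".
- **Rank.** The contrast is secondary in 3.4 and exploratory in 6.2. Section 2.1 nevertheless includes comparison with the control group in the primary objective, and 3.4 and 5.6 present the result as a direct measure of the gain in adherence.
- **Main between-group analysis (6.3.2).** "The primary comparison between the groups will use the creatinine normalized weekly quantitative urine levels for buprenorphine and norbuprenorphine".
- **Masking.** Section 5.2.3 says that "all patients will receive open-label Suboxone® for 12 weeks". No masking of the laboratory, the consultant or the classifying staff is described. Data forms carry study number and initials (8.2).
- **Only adherence threshold.** Section 6.1 gives a tentative 80% of treatment days per participant. That is not a urine rule.

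**The concern.** The AC adherence rate is half of the contrast. It is produced by a step with three unstated parts: the urine cut-off, the way urine combines with self-report, and the status of days without a sample. Only controls pass through this step, and the self-report available daily for them is a text message that only the AC arm sends (3.1). Anyone who combines the two sources can probably tell the arm.

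Choices made under those conditions can move the AC rate, in either direction, with no change in dosing. The result would then be read as the improvement due to remote observation and is a natural input to the later efficacy trial that 3.3 mentions.

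**Working it through.** **1. The plan's own figures, and whether they depend on the calls.** Section 6.1 gives two sets.

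- *Confidence intervals for ROD.* Logit interval: logit(p) ± 1.96 × √(1/x + 1/(n−x)).
  - 18/20: 2.197 ± 1.96 × 0.745, giving 67.6% to 97.5% (stated 68%, 98%).
  - 19/20: 2.944 ± 1.96 × 1.026, giving 71.8% to 99.3% (stated 72%, 99%).
- *Power, 80% at d = 0.65.* Assumptions not in the text: two-sided alpha, 12 weekly points, compound symmetry with correlation 0.4, d reached at the last point. Without dropout the variance of the slope difference is 2 × (1 − 0.4)/(20 × 143) = 0.000420, where 143 is the sum of squared centred times. Power = Φ((0.65/11)/√0.000420 − 1.96) = 82.3%. With 18 per arm throughout it is 78.1%. With retention falling linearly from 20 to 18 it is 80.1%.

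Both sets reproduce. Neither uses an AC adherence call, so this point does not touch them.

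**2. Sensitivity to the cut-off (illustration).** The spread of levels is not in the documents. Assume levels in truly adherent patients are log-normal with SD s on the natural-log scale, and a cut-off at a fraction c of the median. The share of truly adherent samples called non-adherent is Φ(ln c / s).

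| s | c = 10% | c = 30% | Difference |
|---|---|---|---|
| 0.8 | 0.2% | 6.6% | 6.4 points |
| 1.2 | 2.7% | 15.8% | 13.1 points |

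These differences apply to truly adherent samples. If a share a of AC samples is truly adherent, the false loss in the AC urine-based rate is a × difference. Section 1 puts compliance near 50%. With a = 0.5 the loss is 0.5 × 6.4 = 3.2 to 0.5 × 13.1 = 6.6 points. A higher cut-off also catches more truly non-adherent samples, but that is correct classification, not bias.

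**3. Days without a sample.** Table 1 gives 24 urines and 84 dosing days. With full attendance 84 − 24 = 60 days (71%) have no same-day urine. Suppose 20% of AC urines are read as non-adherent (an assumption), that is 24 × 0.2 = 4.8 samples, and leave self-report aside:

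- only the visit day fails: 1 − 4.8/84 = 94.3% adherent;
- the whole 3.5-day interval fails: 1 − (4.8 × 3.5)/84 = 80.0% adherent.

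The same samples give rates 14 points apart, depending on a rule that is not written.

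**4. What re-calls can do with 20 per arm (illustration).** Each AC patient re-called moves a patient-level contrast by 1/20 = 5 points. Take ROD at 18/20 (the 90% case in 6.1) and use Fisher's exact test, which is simpler than the planned mixed model:

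| AC adherent | Difference | p |
|---|---|---|
| 10/20 | 40 points | 0.014 |
| 11/20 | 35 points | 0.031 |
| 12/20 | 30 points | 0.065 |

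In this example two re-calls carry the result across 0.05.

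**The case against.** The strongest reply is that this is an exploratory comparison in a 40-patient preliminary study. The main between-group analysis uses continuous levels from both arms and needs no adherence call, and the ROD video endpoint does not depend on a urine cut-off. That stands, and it limits the weight of the point.

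Several stronger readings are tempting, and the documents do not support them:

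- *The reader knows the arm.* Urine comes from both arms, the consultant sentence in 3.3 is not limited to AC, and nothing says how results reach the consultant. Knowledge of arm is a likely inference from the control-only classification and the AC text messages. It is not a documented fact. The text available for review also lacks a part just before 7.4.3.1, apparently on data and safety monitoring, so masking wording there cannot be excluded.
- *No cut-off exists.* The optimisation sentence in 3.3 concerns a later trial. It is consistent with an unsettled rule but does not show that this trial has no working one. What can be said is that none is stated.
- *The calls are the consultant's alone.* The consultant assists, and self-report is part of the AC rule. The missing combination rule matters as much as the missing cut-off.
- *The AC rate would fall by 6 to 13 points.* That holds only if essentially all AC samples are truly adherent.
- *The calculation measures the effect of unmasking.* It measures sensitivity to the cut-off. A masked reader who chose the higher cut-off would produce the same shift.

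It is also fair to say that masking alone would not repair the contrast, because video in one arm and urine plus self-report in the other are different instruments. The fix therefore has to cover both.

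**Conclusion.** The point holds for the ROD-versus-AC adherence contrast and no further. As written, the control rate depends on unstated rules applied to controls only, in an open-label trial with no described masking, so it can move with judgement by someone who probably knows the arm. The documents show neither that this will happen nor in which direction.

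The size cannot be fixed from the documents. Under the assumed log-normal spread the added miscalls are 6 to 13% of truly adherent samples, or about 3 to 7 points on the AC urine-based rate if half of the samples are truly adherent. The unwritten rule for unsampled days leaves a 14-point range in the 20% example. This is a cheap improvement to a secondary or exploratory result, not a threat to the trial's main comparison.

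**What to change.** Amend 3.3, 3.4 (with the matching text in 5.6) and 6.2 as follows.

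1. Before allocation is linked, write one urine rule: the creatinine-normalized cut-off and how days without a sample are assigned. Fix it in advance, or set it on pooled results without arm labels.
2. Have the consultant apply it to coded samples from both arms, seeing study number only, without initials, arm, self-report or text-message data.
3. Only then combine the urine call with self-report, by a written rule. Since 3.1 describes a daily confirming text for AC only, the rule should say what self-report, if any, enters for ROD.
4. Report the ROD-versus-AC contrast from this common urine-based classification, with results at half and at double the cut-off.
5. Keep the video-verified ROD rate as a separate description.

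The cost is wording plus some consultant time. The samples, the assays and the consultant are already planned, and records are already coded. The downside is that the consultant also classifies the ROD samples, at most 20 × 24 = 480 more results from the medication phase.

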## **3.4 Study Endpoints**

### **3.4.1 Primary Study Endpoint**

For the ROD group, we will calculate the within-patient proportion of study days on which video captured adherence, as per protocol.

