video Skype call with study staff. Data from that study reveal low rates of continued opioid use while on Suboxone® and high rates of Skype-observed doses. All urines tested during the study were buprenorphine positive, demonstrating excellent adherence with the treatment. In addition, self-reports of opiate use corresponded to urine drug screen results, and only one participant continued to test positive for opioids intermittently during the study. ***Participants successfully completed 100% of required in-office visits, and 90% of scheduled Skype calls. Perhaps more important, participants did not find the daily Skype calls to be burdensome.***

However, the pilot study did not have a control group and because the clinic was only open Monday-Friday, we did not observe dosing on the weekends. While this is true for many physician offices and community based treatment providers, it is problematic because weekends are often a high risk time for drug users. It is important to observe dosing 7 days a week in order to ensure optimum adherence and avoid diversion. It is equally important to determine if ROD improves buprenorphine adherence compared to an attention-matched control group.

[name] has developed a protocol that uses a ***smartphone to video record buprenorphine dosing and automatically sends this recording through HIPAA compliant means to clinical staff who can then review it at a convenient time and location.*** Her protocol also uses SMS text messaging to communicate with patients. To address the feasibility of patients with an OUD using this technology, [name] conducted a pilot study with 71 patients in OUD treatment locally regarding the feasibility and usability of such a technology. The preliminary data indicated:

- While 95% of patients had a cell phone, the majority of them (76%) had “pay as you go” plans with limited data capabilities. In addition, 71% reported changing their cell phone regularly.
- 87% reported sending and receiving SMS text messages daily, 60% used the video option on their phones to send videos, 54% watched videos online, and 53% used an “instant message app”.
- 78% reported they would take part in a text messaging program to help prevent relapse and 75% reported they would be receptive to a cell-phone based OUD intervention.

***These findings suggest using the proposed platform to monitor buprenorphine dosing is both feasible and would be welcomed by patients undergoing opioid treatment.***

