## **3 Investigational Plan**

Forty patients with OUD, who are not currently prescribed buprenorphine, will be recruited through the University of Pennsylvania's Center for the Studies of Addiction (CSA), an outpatient substance abuse treatment facility. Potential participants will be screened for physical and psychological appropriateness for inclusion in the study using the CSA standard intake procedures. This includes a psychosocial diagnostic evaluation, a medical exam, urine and blood tests, and an EKG (see Measures for full description of screening assessments). Participants who are appropriate for the trial will be inducted onto Suboxone® using standard office based induction as described in the ASAM National Practice Guideline for the Use of Medications in the Treatment of Addiction Involving Opioid Use (Kampman and Jarvis 2015).

All patients will receive buprenorphine (Suboxone®; up to 24 mg daily) and will be randomly assigned to one of two groups. The experimental group (n=20) will receive daily remote observed dosing (ROD) via a secured video platform that records dosing using study-provided smartphones (approximately 5 minutes each session). ROD videos will be monitored daily for compliance. The attention control group (AC, n=20) dosing will not be observed. All subjects will attend 2 weekly study visits (3 study visits during the induction phase in Week 2). Study visits starting in Week 3, after the Induction phase, will consist of counseling in the form of weekly Medication Management (MM); buprenorphine distribution with medication management; and a urine screen. Study visit 4 will consist of a urine screen and phone management task (downloading study related videos) for those randomized to the Remote Observed Dosing Group.

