### **6 Statistical Plan**

#### **6.1 Sample Size and Power Determination**

One target of the study is to estimate the proportion of participants in the ROD group who adhere with their medication schedule for, say, 80% or more of their treatment days. If 90% of the 20 participants adhere, then our data will yield a 95% confidence interval of (68%, 98%) for the proportion adhering; if 95% are adherent, then our confidence interval will be (72%, 99%).

CONFIDENTIAL

For the longitudinal comparisons of quantitative (nor)buprenorphine levels, transformed so that a linear model is appropriate, we use the methods of Hedeker and colleagues. For an alpha level of 0.05, and assuming a within subject correlation of 0.4, and dropout of 10%, the sample size provides 80% power for a standardized linear group by time effect of  $d=0.65$ . Thus, the study is powered for medium to large effects in quantitative buprenorphine levels.

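### The ROD adherence endpoint scores a dose taken but not filmed as non-adherent, so it is a lower bound, and it is compared with AC and prior-study rates that carry no filming requirement.

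*Combined protocol and SAP*

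**What the plan says.** Section 3.4.1 defines the primary endpoint for the ROD group: "we will calculate the within-patient proportion of study days on which video captured adherence, as per protocol". Sections 2.1, 5.6 and 6.2 repeat the definition. Section 3.3 (Video Compliance) has submissions logged by date and time and checked daily, with files copied from the memory card at office visits. No section says how to score a day with no video, and none lets urine or self-report reclassify one.

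The AC group is handled differently. Sections 3.4 (secondary endpoints), 5.6 and 6.2 classify each AC day from self-report combined with (nor)buprenorphine levels, then compare that rate with the video-verified ROD rate. Sections 3.4 and 5.6 present the result as estimating the gain in adherence directly. Section 6.2 also sets the ROD rate against prior studies, which 1.1 describes in terms of positive urine at visits, days on which medication was taken, and claims data.

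Section 6.1 names as one target "the proportion of participants in the ROD group who adhere with their medication schedule for, say, 80% or more of their treatment days". On the feasibility pilot, 1.1 reports "Participants successfully completed 100% of required in-office visits, and 90% of scheduled Skype calls" and also "All urines tested during the study were buprenorphine positive, demonstrating excellent adherence with the treatment".

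**The concern.** The quantity of interest in 2.1 and 6.1 is whether the medication was taken. The endpoint measures something narrower: the medication was taken and a usable recording exists. A forgotten recording or a lost or uncharged phone gives the same score as a missed dose. The memory-card copy rescues only videos that were recorded.

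The gap falls on one arm. An unfilmed ROD dose cannot count, whereas an AC dose can count without video. This is an asymmetry of measurement between the two groups being compared, and it also affects the comparison with prior studies. Section 3.3 says that data from this trial will inform a later efficacy trial. For that purpose a filming failure and a dosing failure call for different responses, and the planned summary does not separate them.

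**Working it through.** **Inputs.** ROD group of 20 (section 3). 84 days of video or attention control (Table 1). An 80% level (6.1). In the pilot, 90% of scheduled calls completed and all urines positive (1.1). Adherence of 93% and 96% in the recorded-video tuberculosis study (1.1).

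**1. The plan's own figures.** Section 6.1 gives 95% intervals of (68%, 98%) for 90% of 20 and (72%, 99%) for 95% of 20. A Wald interval on the logit scale is logit(p) ± 1.96 × √(1/x + 1/(n − x)), back-transformed.
- 18/20: 2.197 ± 1.96 × 0.745 gives (67.6%, 97.5%).
- 19/20: 2.944 ± 1.96 × 1.026 gives (71.8%, 99.3%).

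Three limits agree on rounding. The fourth is 97.49% before rounding, about half a point below the stated 98%. None of the five other methods tried (Wald, Wilson, Agresti-Coull, Jeffreys, Clopper-Pearson) comes as close in both scenarios. The stated widths are sound; the issue is which proportion they would be centred on.

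**2. What 80% on video means in true adherence.** Let c be the probability that a taken dose is captured. If capture does not depend on the day, the expected video rate is (true adherence) × c, so 80% on video corresponds to true adherence of 0.80/c.

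The pilot does not give c directly, because it is unknown how many missed-call days were dosed. Let f be the share that were. Then c = 0.90/(0.90 + 0.10f).

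| f | c | 0.80/c |
|---|---|---|
| 0 | 100% | 80.0% |
| 0.25 | 97.3% | 82.2% |
| 0.50 | 94.7% | 84.4% |
| 0.75 | 92.3% | 86.7% |
| 1 | 90.0% | 88.9% |

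If the tuberculosis rates are taken as capture rates, 0.80/0.96 = 83.3% and 0.80/0.93 = 86.0%.

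**3. Understatement of the mean rate.** With 90% of days observed, true adherence is 0.90 + 0.10f, that is 90% to 100%. The video rate is therefore 0 to 10 points too low.

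**4. Effect on one patient's chance of reaching 80%.** 0.80 × 84 = 67.2, so 68 days are needed. The table takes the upper-end case c = 0.90 and independent days, using the binomial P(X ≥ 68) with n = 84.

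| Doses taken | True chance of reaching 80% | Chance on video |
|---|---|---|
| 95% | above 99.9% | 91% (p = 0.95 × 0.90 = 0.855) |
| 90% | 99.6% | 57% (p = 0.81) |
| 85% | 88% | 20% (p = 0.765) |

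For the 90% patient, the chance on video is 80% at c = 0.93 (p = 0.837) and 94% at c = 0.96 (p = 0.864).

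**5. Patients who take every dose.** With the same c = 0.90 for everyone, 99.6% reach 68 videos. If c varies between patients (beta distribution, mean 0.90, SD 5, 10 or 15 points, all assumed), 93%, 84% or 82% do. With 20 patients, each misclassified patient moves the group figure by 1/20 = 5 points.

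**The case against.** A reader might infer that the 80% target is in effect 89%. The documents do not support that; it is the top of the range. Pilot office visits were weekly and included an observed dose, so positive urines do not show that a dose was taken on each missed-call day. The pilot used live, scheduled weekday calls, whereas this trial uses self-recorded video seven days a week with a memory-card backup. Section 1.1 calls the proposed method very similar to the recorded-video studies, so 93% to 96% may be the closer guide. Section 6.1 offers 80% only as an example and does not say that video decides it. That link is an inference, though a fair one: video is the only daily ROD adherence measure planned.

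A reader might also infer that the trial would wrongly judge ROD a failure. No success rule is attached to the 80% level. Even 82% to 93% of fully dosed patients passing lies within both intervals in 6.1 and far above the prior rates of 48%, 41% and 32%.

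Counting only observed doses is defensible where observation is the intervention and reducing diversion is an aim. The submission log should already allow an absent video to be told apart from one showing no dose. All of this stands, and it limits the size. It does not remove the asymmetry with AC, and the plan neither states the counting rule nor labels the result as video-confirmed only. With the rule unstated, an analyst could instead drop unfilmed days, which would change the denominator and could push the result the other way.

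**Conclusion.** The concern holds as a measurement asymmetry of modest and uncertain size. The ROD rate is a lower bound on adherence, provided that a filmed dose is a dose taken. The ROD-versus-AC adherence comparison and the prior-study comparison understate ROD whenever doses are taken unfilmed.

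At the pilot's observation rate, the 80% level corresponds to 80% to 89% true adherence, or 83% to 86% at the tuberculosis study's rates. These figures assume that the cited rates carry over and that capture is unrelated to the day. The between-patient spread in capture is an assumption with no source in the documents.

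The finding does not reach the primary between-group comparison (6.2, 6.3.2), which uses creatinine-normalised urine levels and does not depend on filming. Nor does it make the interval widths in 6.1 wrong.

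**What to change.** In 3.4.1, 5.6 and 6.2:

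1. Code each ROD day as dose seen on video, video shows dose not taken, or no usable video.
2. State that days without a usable video count as non-adherent in the main figure, and label it video-confirmed adherence (lower bound).
3. Prespecify a sensitivity analysis that classifies ROD days by the same self-report plus (nor)buprenorphine rule used for AC. Apply it in both directions, so that an unfilmed day can be upgraded and a filmed day contradicted by urine can be downgraded.
4. Report the proportion reaching 80%, the ROD-versus-AC comparison and the prior-study comparison under both definitions. Neither should be the sole basis for the prior-study comparison.

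**Cost.** A code on the daily video log and further tabulations from urine already collected. The AC rule must be written out in enough detail to apply to both arms, including how changes in dose affect the expected level. In AC the obvious self-report source is the daily confirmation text (3.1). No equivalent is described for ROD, so a question on unfilmed days at each visit would be needed.

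**Downside.** Two figures are reported instead of one. The urine-supported figure is less strict and cannot date individual doses, so it belongs as a sensitivity analysis.
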